5. ENDPOINTS

5.1 PRIMARY ENDPOINT

CTP: *Total cell count of neutrophils in Bronchoalveolar Lavage (BAL) after 24 hours of the segmental endotoxin challenge.*

For detailed information regarding the determination of this primary endpoint please refer to Section 5.3 of this TSAP.

5.2 SECONDARY ENDPOINTS

5.2.1 Key secondary endpoints

This section is not applicable as no key secondary endpoints have been defined in the CTP.

5.2.2 Secondary endpoints

CTP: *Total and differential cell count of neutrophils (only differential cell count), eosinophils, monocytes, macrophages and lymphocytes in BAL after 24 hours of the segmental endotoxin challenge.*

For detailed information regarding the determination of these secondary endpoints please refer to Section 5.3 of this TSAP.

Differential (i.e. relative) cell count of neutrophils, eosinophils, monocytes, macrophages and lymphocytes will be determined using the method of cytospin microscopy. The total cell count of non-squamous cells, which will be determined in a microscopic counting chamber, is the denominator of the differential cell counts. Multiplication of the differential cell counts determined by cytospin microscopy ($\text{differential}_{\text{any, microsc}}$) with the total cell count of non-squamous cells ($\text{total}_{\text{non-squamous cells, microsc}}$) will result in the total cell count for the various cell types ($\text{total}_{\text{any, derived}}$). Furthermore the total cell count for the various cell types will be standardised to the retrieved BAL volume ($\text{total}_{\text{any, derived, standardised}}$). These differential and total cell counts for the various cell types will be analysed as primary, secondary and further endpoints:

For neutrophils, eosinophils and lymphocytes (primary, secondary and further endpoints):

$$\text{total}_{\text{any, derived, standardised}} = \text{differential}_{\text{any, microsc}} * \text{total}_{\text{non-squamous cells, microsc}} / \text{BAL volume}$$

The differential cell count of macrophages plus monocytes ($\text{differential}_{\text{macro+mono, derived}}$) will be derived as the sum of differential cell counts of monocytes ($\text{differential}_{\text{mono, microsc}}$) plus macrophages ($\text{differential}_{\text{macro, microsc}}$) from cytospin microscopy. The total cell count of macrophages plus monocytes ($\text{total}_{\text{macro+mono, derived, standardised}}$) will then be derived by multiplying the derived differential cell count with the total cell count of non-squamous cells standardised to the retrieved BAL volume. The derived differential and total cell counts of macrophages plus monocytes will be analysed as secondary [REDACTED] endpoints:

For macrophages plus monocytes (secondary [REDACTED] endpoints):

$$\text{differential}_{\text{macro+mono, derived}} = \text{differential}_{\text{mono, microsc}} + \text{differential}_{\text{macro, microsc}}$$

$$\text{total}_{\text{macro+mono, derived, standardised}} = \text{differential}_{\text{macro+mono, derived}} * \text{total}_{\text{non-squamous cells, microsc}} / \text{BAL volume}$$

The differential cell count of monocytes will in addition be determined using flow cytometry which is more accurate due to immunostaining (CD14). Thus, the differential cell counts of CD14-positive monocytes will be analysed as secondary [REDACTED] endpoints and will be used for derivation of the total cell counts of the monocytes ($\text{total}_{\text{mono, derived}}$), which will also be analysed as secondary [REDACTED] endpoints. This total monocyte cell count will be derived by multiplying the differential cell count of CD14-positive monocytes ($\text{differential}_{\text{mono, flow}}$) with the total cell count of non-squamous cells:

For monocytes (secondary [REDACTED] endpoints):

$$\text{total}_{\text{mono, derived, standardised}} = \text{differential}_{\text{mono, flow}} * \text{total}_{\text{non-squamous cells, microsc}} / \text{BAL volume}$$

In addition the total cells in BAL before segmental challenge, 24 hours after segmental endotoxin challenge and 24 hours after segmental saline challenge will be analysed. They are derived according to:

$$\text{total cells}_{\text{standardised}} = \text{total}_{\text{non-squamous cells, microsc}} / \text{BAL volume}$$

[figure not shown]
The unit of the reported total cell counts for each cell type and for total cells will be $10^3/\text{mL}$.

[figure not shown]
For the inferential statistical analysis of the primary and secondary endpoints, log transformed data will be used and subjects with zero values will not be considered in the inferential analysis of the respective cell type. To overcome a reduced sample size for this situation, for all cell types that have a zero cell count at Visit 7 in the LPS challenged segment, this value will be “imputed” with a small value for the ease of log transformation. To minimize the impact of such “imputation”, we will use 1/10th of the roundup value of the minimal non-zero value of the total cell count observed in the data for each cell type. For the differential cell count of all cell types 0.01 will be added onto the zero values. This imputation strategy will only be applied to the data which will be inferentially analysed. The descriptive analysis will be based on the actual data.

Further endpoints related to safety assessment:

- *Number (%) of subjects with treatment emergent adverse events (TEAE).*
- *Number (%) of subjects with drug related AEs*

■ [REDACTED]

5.4.5 Other safety parameters

5.4.5.1 Physical examination findings

Results of physical examination will not be analysed as a specific endpoint. Clinically significant findings will be reported as baseline conditions or adverse events (AEs), cf. Section 5.3.1 of the CTP, and will be analysed as such.

5.4.5.2 Vital signs

CTP: Systolic and diastolic blood pressure (BP) and pulse rate (PR) will be measured after the subject has rested for at least 5 minutes in a supine position.

5.4.5.3 Safety laboratory parameters

Cf. CTP Section 5.3.3 for a definition of safety laboratory parameters assessed in this trial. Urine dipstick data will not be included in the database.

5.4.5.4 Electrocardiogram

Results from electrocardiogram (ECG) will not be analysed as a specific endpoint. Relevant ECG findings will be reported as AEs and will be analysed as such.

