## CLINICAL TRIAL PROTOCOL SYNOPSIS

Name of company:		Boehringer Ingelheim	
Name of finished product:		N/A	
Name of active ingredient:		BI 1026706	
Protocol date: 06 Aug 2015	Trial number: 1320.17		Revision date: 19 Dec 2016
Title of trial:	A randomized, double-blind, placebo-controlled, parallel group, Phase I trial in healthy current smoker subjects to assess pharmacodynamic effects on segmental endotoxin induced inflammatory response and safety of 4 weeks oral administration of BI 1026706		
Principal Investigator:	[REDACTED], MD. [REDACTED] Tel: [REDACTED] Fax: [REDACTED]		
Trial site(s):	single center trial		
Clinical phase:	I		
Objective(s):	The primary and secondary objectives of the current study are the assessments of anti-inflammatory pharmacodynamic effects on segmental endotoxin induced inflammatory response after 4 weeks treatment with BI 1026706. Further objectives are to evaluate the pharmacokinetics and safety of BI 1026706		
Methodology:	Randomized, double-blind, placebo-controlled, parallel group, 4 weeks treatment of 100 mg BI 1026706 or placebo b.i.d. prior to segmental bronchial LPS challenge, single center		
No. of subjects:			
total entered:	50		
each treatment:	25 subjects per arm		
Diagnosis :	Healthy volunteers		
Main criteria for inclusion:	Volunteers of both sex with females being of non-childbearing potential, age $\geq 18$ and $\leq 65$ years, current smokers with at least 1		

Name of company:		Boehringer Ingelheim	
Name of finished product:		N/A	
Name of active ingredient:		BI 1026706	
Protocol date: 06 Aug 2015	Trial number: 1320.17		Revision date: 19 Dec 2016
	cigarette per day over the last 12 months and a smoking history of at least 1 pack year, healthy as assessed by the investigator on a screening examination, FEV1 > 80% and FEV1/FVC > 70% predicted, BMI range: $\geq 18.5$ and $\leq 29.9$ kg/m  , negative drug screen, positive cotinine test		
Test product:	BI 1026706 film-coated tablet for oral administration (formulation A1)		
dose:	100 mg b.i.d.		
mode of administration:	Oral administration		
Comparator products:	Placebo film-coated tablet for oral administration (formulation A1)		
dose:	Not applicable		
mode of administration:	Oral administration		
Duration of treatment:	28 days		

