#### 5.3.4 Electrocardiogram

12-lead ECGs (I, II, III, aVR, aVL, aVF, V1 - V6) will be recorded using the ECG machine of the investigator site. For time points refer to the Flow Chart.

[Redacted]

The ECG records will be checked for pathological results by the investigator or a designee. Clinically relevant abnormal findings as judged by the Investigator will be reported as adverse events (please refer to [Section 5.3.6](#)).

For the inclusion or exclusion of a subject and for the assessment of cardiac safety during the study, the QT and QTcB values generated by the ECG machines or their manual corrections by the investigators will be used.

Any ECG abnormalities will be carefully monitored and, if necessary, the subject will be removed from the trial and medically treated. Baseline measurements will be defined as the measurements taken prior to the first administration of trial medication.

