## 5.7 APPROPRIATENESS OF MEASUREMENTS

Measurements performed during this trial are standard measurements and will be performed  to monitor safety aspects in an appropriate way.

The PK parameters and measurements outlined in [Section 7.3.5](#) are generally used as measurements to assess drug exposure.

The scheduled measurements are appropriate to see drug induced changes in vital signs, lung function, standard laboratory values and ECG.

These primary and secondary endpoints are standard and accepted for evaluation of pharmacodynamic parameters of an oral drug, and they are widely used in this kind of studies.

Therefore, the appropriateness of all measurements applied in this trial is given.

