## 7.2 NULL AND ALTERNATIVE HYPOTHESES

This trial will be conducted to detect statistically significant differences between BI 1026706 and placebo in BAL neutrophil counts 24 hours following endotoxin challenge at the end of treatment.

The null and alternative hypotheses are

$H_0$ : geometric mean ratio of neutrophil counts at the end of the treatment is 1.

$H_a$ : geometric mean ratio of neutrophil counts at the end of the treatment is not equal to 1.

[figure not shown]
Safety and tolerability of BI 1026706 is to be determined on the basis of the safety assessments in comparison to placebo. It is not planned to test any statistical hypotheses with regard to these variables in a confirmatory sense. Instead, they will be described in their entirety and evaluated by descriptive statistical methods.

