4. CHANGES IN THE PLANNED ANALYSIS OF THE STUDY

All analyses described in the TSAP are outlined in the CTP and its amendments.

In addition to what has already been outlined in the CTP, the following changes in the analyses are introduced in this TSAP:

- Differential (i.e. relative) cell count of neutrophils, eosinophils, monocytes, macrophages and lymphocytes, as well as the total cell count of non-squamous cells in BAL will be determined using the method of cytospin microscopy. Since it is not possible with this method to clearly differentiate between macrophages and monocytes, the secondary and further endpoints regarding the cell type macrophages will actually present the total and differential cell count of macrophages and monocytes together and will be named as such in the analyses.

Note, the secondary [redacted] endpoints regarding the cell type monocytes used in the analyses are based on the differential cell count determined using flow cytometry which is more accurate due to immunostaining (CD14).

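### The SAP routes ECG only through adverse events, so a group-level shift in PR, QRS or QTcB would appear in no planned summary table

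*SAP*

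**What the plan says.** Protocol:

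- Synopsis: safety is among the further objectives ("Further objectives are to evaluate the pharmacokinetics and safety of BI 1026706"), and the 12-lead ECG is one of the safety criteria.
- Flow Chart: ECGs at Visits 1, 2, 4, 6, 7 and 8.
- Section 5.3.4: besides eligibility, QT data serve the trial itself: "for the assessment of cardiac safety during the study, the QT and QTcB values generated by the ECG machines or their manual corrections" are to be used. It also fixes an ECG baseline: "Baseline measurements will be defined as the measurements taken prior to the first administration of trial medication". Findings the investigator judges clinically relevant become AEs.
- Section 5.7: "The scheduled measurements are appropriate to see drug induced changes in vital signs, lung function, standard laboratory values and ECG".
- Section 7.2: no confirmatory testing of safety variables; instead "they will be described in their entirety and evaluated by descriptive statistical methods".
- Section 7.3.4: covers the assessments in Section 5.3, plans descriptive statistics for continuous data, and names ECG with vital signs and laboratory parameters as measurements to be assigned to treatment. The same section says relevant ECG findings go in as AEs.

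SAP:

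- Section 5.4.5.4: "Results from electrocardiogram (ECG) will not be analysed as a specific endpoint"; relevant findings are handled as AEs.
- Section 7.8.4: one sentence, again giving only the AE route.
- Sections 7.8.2, 7.8.3 and 7.8.5.2: laboratory values, vital signs (including pulse rate) and lung function are summarised over time and as change from baseline.
- Section 4: "All analyses described in the TSAP are outlined in the CTP and its amendments"; the changes listed there concern BAL cell counting only.

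**The concern.** An AE-based analysis picks up an ECG effect only when an investigator finds one subject's tracing clinically relevant. A drug effect on conduction or repolarisation may instead be a modest shift in most subjects, with each tracing still unremarkable by itself. Such a shift shows in the mean change from baseline by arm, and the SAP plans no such summary for ECG.

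The protocol presents its ECG schedule as able to show drug-induced change and collects a pre-dose value with repeated values on treatment. At stake is whether the trial can describe ECG intervals by arm after up to four weeks of dosing, or can report only how many subjects had an ECG-related AE. Neutrophil inference is not at stake.

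**Working it through.** **1. Side-by-side reading of the SAP**

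| Assessment | Relevant findings become AEs | Summary over time and change from baseline |
|---|---|---|
| Laboratory (7.8.2) | yes | yes |
| Vital signs (7.8.3) | yes | yes |
| Lung function (7.8.5.2) | not stated there | yes |
| ECG (5.4.5.4, 7.8.4) | yes | none planned |

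For laboratory data and vital signs the AE route and the value summaries sit together, so the AE route alone does not explain why ECG has no summary. ECG is also absent from the data types given analysis phases in SAP 6.1 and from the baseline examples in SAP 6.7.

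**2. The plan's own figures**

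The documents give no ECG variance, precision or power. Their one power statement concerns neutrophils: at least 84% with 22 evaluable per group, fold-change 1.5, CV 0.53, one-sided 5% (Protocol 7.7). It reproduces:

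- SD on the log scale = sqrt(ln(1 + 0.53²)) = 0.498
- SE = 0.498 × sqrt(2/22) = 0.150
- noncentrality = ln(1.5)/0.150 = 2.70
- noncentral t power on 42 df = 84.5%

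For ECG this supplies only the group sizes: 25 entered, or 22 as a lower illustration.

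**3. What a by-arm summary could show (assumed SDs)**

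Half-width of the 90% CI for the between-arm difference in mean QTcB change = t(0.95, 2n−2) × SD × sqrt(2/n). With n = 25 and t = 1.677:

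- SD 15 ms: SE = 15 × sqrt(2/25) = 4.24 ms; half-width 7.1 ms
- SD 20 ms: SE = 20 × sqrt(2/25) = 5.66 ms; half-width 9.5 ms

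With n = 22 the half-widths are 7.6 and 10.1 ms. If a 10 ms shift were tested one-sided at 5%, power would be 75% (SD 15) or 54% (SD 20) with 25 per arm, and 70% or 49% with 22. This is useful description but not sharp detection.

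**4. What a threshold on single tracings would show (assumed values)**

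Assume one ECG per subject, 25 treated subjects, normally distributed QTcB with mean 400 to 410 ms and SD 15 to 20 ms, and a 10 ms drug shift. The expected number above 450 ms is 25 × P(Z > (450 − mean − 10)/SD):

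- mean 400, SD 15: z = 40/15 = 2.67, giving 0.1 subjects
- mean 410, SD 20: z = 30/20 = 1.50, giving 1.7 subjects

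Without the shift the same two settings give 0.01 and 0.6. So a 10 ms shift could add about one subject or fewer above 450 ms. The AE rule is clinical judgement, not a 450 ms cut-off, so this only illustrates how little individual tracings may reveal.

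**The case against.** The strongest case is that the SAP follows the protocol. The one visible ECG-specific sentence in protocol 7.3.4 is the AE rule, and the SAP nearly repeats it. Section 5.3.4 can be read as individual monitoring: its QT sentence opens with eligibility and settles which values count, and the next paragraph concerns watching and, if necessary, removing a subject. On that reading SAP section 4 had nothing to declare.

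Much of this stands, and it rules out several stronger readings a reader might infer:

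- **An undeclared departure from the protocol.** Not supported. The AE route is in the protocol, part of 5.3.4 is redacted, and the SAP quotes protocol sentences on weight, laboratory highlighting and lung function that are absent from the public text. A sentence on ECG analysis could be hidden in the same way.
- **All ECG values are discarded, or a shift could not be seen at all.** Not supported. SAP section 7 has a general provision for listing each subject's values. SAP 5.4.5.3 and 5.4.5.6 keep urine dipstick and oxygen saturation out of the database but say no such thing of ECG. A listing, however, is not a comparison of arms.
- **The pre-dose ECG has no purpose without group tables.** Not so; it lets the investigator judge later tracings in the same subject.
- **A known QT concern.** Exclusions 11 and 12 are eligibility screens, and the only visible AESI is hepatic injury.

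What the objection does not remove is the general commitment in 7.3.4 to describe continuous safety data, with ECG named among the measurements, or the unexplained contrast with the other safety data.

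**Conclusion.** The point holds as a gap in the planned safety summaries. On the visible text, a group-level change in PR, QRS or QTcB that no investigator calls relevant would be in no planned summary table. Heart rate is not part of the gap, because pulse rate is summarised with vital signs.

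Severity is minor to moderate: the trial is exploratory, safety is a further and descriptive objective, and the primary analysis is unaffected. The half-width of about 7 to 9.5 ms rests on an assumed SD of change of 15 to 20 ms and 25 per arm. It supports a descriptive table, not a claim that the trial could reliably detect or exclude a 10 ms effect.

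**What to change.** In SAP 5.4.5.4 and 7.8.4, add:

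- Descriptive statistics by treatment and visit for PR, QRS, QT and QTcB, and for their change from the last pre-dose ECG.
- The number of subjects per arm with on-treatment QTcB above 450 ms. This value is the example in exclusion criterion 11, used here only as a reporting cut-off.
- Separate display of Visits 4 and 6 from Visits 7 and 8. Protocol 6.2.4 places the relevant Flow Chart procedures at Visit 6 before the bronchoscopy, while Visits 7 and 8 follow the LPS challenge. Mixing them would blur drug and procedure.

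No heart-rate table and no hypothesis test are needed. If the sponsor prefers to keep the AE route alone, the SAP should at least say that ECG values are not summarised, and why.

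Cost: one or two extra tables and no new measurement. If the intervals are not in the eCRF, they must be entered and checked from existing printouts: up to 50 subjects × 6 ECGs = 300 recordings, or 300 × 4 = 1,200 values.

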5.4.5.5 Pulmonary function testing

[figure not shown]
The highest FEV₁ and FVC from 3 blows as well as the time point of the first pulmonary function testing maneuver will be recorded in the eCRF.

5.4.5.6 Oxygen saturation

CTP: *Oxygen saturation will be measured by single finger pulse oximetry while conducting bronchoscopies.* However, oxygen saturation data will not be included in the database.

5.4.5.7 Adverse events

- Number (%) of subjects with serious AEs (SAEs)
- Number (%) of subjects with AEs of special interest (AESIs).
- Number (%) of subjects with other significant AEs (according to ICH E3)

6. GENERAL ANALYSIS DEFINITIONS

6.1 TREATMENTS

For basic study information on treatments to be administered, assignment of dose groups, and selection of doses, cf. Section 4 of the CTP.

Subjects will be treated with either

- 100 mg BI 1026706 (test treatment, T) or
- placebo (reference treatment, R),

twice daily for 28 +/- 2 days.

The following separate study analysis phases will be defined for the analyses of AEs, laboratory tests, vital signs and body weight:

- **Screening** (ranging from 0:00 h on day of informed consent until first administration of study drug)
- **On treatment** (separately for each treatment, ranging from the time of first study drug administration [REDACTED] 4 days after the last administration of study drug; note that 4 days after the last trial medication application are defined in CTP Section 5.3.7 as the residual effect period [REP])
- **Post-treatment** (separately for each treatment, ranging [REDACTED] days after the last administration of study drug, i.e. the end of the REP, to start of post-study phase)
- **Post-study** ([REDACTED] after the last administration of study drug or at 0:00 h on the day after the EOT visit, whichever is later)

Note that the post-treatment phase might not exist for individual subjects, e.g. if the EOT visit is [REDACTED] of the last administration of study drug.

Table 6.1: 1 Flow chart of study analysis phases for adverse events, laboratory tests, vital signs and body weight

Study analysis phase	Start	End
Screening	Date of informed consent	Date/time of first administration of study drug
On treatment	Date/time of first administration of study drug	Date/time of last administration of study drug + REP, [REDACTED] * 24 h
Post-treatment ¹	Date/time of last administration of study drug + REP ([REDACTED] * 24 h)	12:00 AM on day after trial completion date
Post study	Date/time of last administration of study drug + REP ([REDACTED] * 24 h) or 12:00 AM on day after trial completion date (whichever is later)	Not defined – a placeholder date is used, e.g. a date after database lock

¹ does not necessarily exist

Displays of AEs, laboratory tests, vital signs and body weight will be presented separately for the treatments, labelled "**BI 1026706**" and "**Placebo**".

CTR Section 15, Appendix 16.1.9.2.8.2 and Appendix 16.1.9.2.8.3 AE displays will present results for these study treatments during on-treatment phases only, labelled as indicated above. Screening, post-treatment and post-study periods will not be included in this analysis.

CTR Appendix 16.1.9.2.8.1 displays will present results for the following study analysis phases:

- Screening
- On-treatment (separately per study treatment listed above, labelled with the name of the respective study treatment)
- Post-treatment (separately per study treatment listed above, labelled "**Post-BI**" and "**Post-Placebo**")
- Post-study

In CTR Section 15 AE tables and CTR Appendix 16.1.9.2.8.1 displays, a total over both on-treatment phases (i.e., BI 1026706 plus placebo, labelled "**Total on-trt**") will be provided in addition.

In CTR Appendix 16.1.9.2.8.1 displays, a total over all study phases (labelled "**Total**") will be provided in addition.

No total columns will be provided in CTR Appendices 16.1.9.2.8.2 and 16.1.9.2.8.3.

Displays of laboratory tests, vital signs and body weight will present results by study treatment.

More details on the technical implementation of these analyses are provided in the analysis data set (ADS) Plan of this TSAP.

